2. STUDY OBJECTIVES

2.1 PRIMARY AND SECONDARY OBJECTIVES

- To develop a set of well-tolerated, robust and reproducible (validated) nasal challenge systems with microbial constituents and allergen. To identify biomarker signatures following different challenges.

- To document a dose response and time course to nasal challenge in terms of cytokine and chemokine release, and nasal epithelial curettage (Rhinoprobe) mRNA expression, cell influx by flow cytometry.
- To provide a set of nasal challenge methods to enable a “proof of target pharmacology” for a novel therapy or vaccine. This may also permit dosage optimisation in relation to clinical efficacy studies.
- To develop real time sampling utilising a special probe that touches the surface of the nasal lining and is linked to a mass spectrometer.

To assess nasal cytokines/chemokines in the nasal mucosa and assess levels of circadian-associated gene expression (BMAL-CLOCK genes) in curettage samples after NAC before and after Vitamin D supplementation.

3. STUDY DESIGN (See Figures above)

Group 1: Nasal challenge with TLR Agonists: This part of the study has a total of 96 subjects divided into two parts; Part A and B.

Part A: We shall have 3 cohorts of 8 healthy volunteers (4 of the 8 having atopy). There will be a separate cohort of 8 subjects for each challenge agent (MPLA, poly-ICLC, and resiquimod).

A careful incremental ascending dose tolerability study will be performed: starting with saline and then giving single doses of 10, 100, 500µg and up to 1000µg of a given challenge agent in volumes ranging from 100µl to 500µl per nostril.

Part A, N= 24

- | | |
|---------------|-------|
| a. MPLA | n = 8 |
| b. Poly-ICLC | n = 8 |
| c. Resiquimod | n = 8 |

For each challenge agent we shall initially take serial SAM samples over 8 hours, and assess the cytokine and chemokine response.

Part B: When we have defined the top safe dose, we shall study up to a further 16 subjects for each challenge agent (up to 46 for resiquimod): and include extra sampling for nasal curettage and blood flow cytometry. For those volunteers in the resiquimod arm of the study, we will invite some of the participants (up to 6 in each group) for a repeat challenge at least 6 weeks after the prior challenge. In January 2016 we updated the protocol to move to a weight based dosing regimen for administering resiquimod. We intend to challenge 6 volunteers (mix of healthy volunteers and those with allergic rhinitis) at a dose of 0.02µg/kg per nostril, which equates to 1µg/100µl per nostril in a 50kg volunteer. For the asthma group, we intend to challenge 4 people at half the dose given to the healthy group. The maximum tolerated dose will then be used for the remaining subjects in the study, [We will not use resiquimod at a dose higher than 10µg/100µl per nostril for the remainder of the study.](#)

Part B, N = 90

- | | |
|---------------|--|
| a. MPLA | n = 16 |
| b. Poly-IC | n = 16 |
| c. Poly-ICLC | n = 16 |
| d. Resiquimod | n = 46 (12 healthy, 12 atopic, 16 allergic asthmatic, 6 non-allergic asthma) |

Group 2: Nasal challenge with tuberculin: This part of the study has a total of 32 subjects divided into two parts; Part A and B.

Part A: This involves 4 cohorts of subjects with defined latent TB.

A careful incremental ascending dose tolerability study will be performed: starting with single doses of:

Part A, N=16

- A. Subjects with Latent TB
 - a. 0.1 TU/100µl/nostril, n = 4
 - b. 1.0 TU /100µl/nostril, n = 4
 - c. 2.0 TU /100µl/nostril, n = 4
 - d. 5.0 TU /100µl/nostril, n = 4

For each agent we shall look at tolerability and initially take serial SAM samples over the next 7 days to assess the cytokine and chemokine response.

Part B: When we have defined the top safe dose, we shall study up to a further 16 subjects with the top tuberculin dose: and include extra sampling for nasal real time mass spectrometry, nasal curettage and blood flow cytometry.

Part B, N=16

- A. Subjects with Latent TB,
 - a. 10.0 TU /100µl/nostril, n = 8
- B. Healthy volunteers,
 - b. 10.0 TU /100µl/nostril, n = 8

Group 3: Nasal challenge with allergen (Timothy grass pollen): This part of the study has a total of 70 subjects divided into two parts; Part A and B.

Part A Nasal challenge with allergen and vitamin D3 supplementation or placebo:

This involves a total of 24 subjects who are allergic to grass pollen and are vitamin D insufficient. Participants are divided into 2 groups (vitamin D supplementation and placebo arms). This is a randomized, double-blind, placebo-controlled study. They will have two NAC; one before and one after supplementation. At each NAC visit, subjects will be given a single dose of Timothy grass pollen (*Phleum P5*) allergen:

The *Phleum P5* is given as 5000 SQ-U = 1µg/100µl per nostril.

After being randomized into one of the two groups they will receive their first NAC and subsequently take vitamin D3, 4000IU (n=18) or placebo (n=6) orally once daily at approximately the same time each morning until their second NAC. This second NAC will take place between 28-35 days. During both days of NAC, serial SAM samples will be taken and nasal curettage performed. Blood samples will also be taken for routine safety tests, peripheral blood mononuclear cells (PBMC) *in vitro* assays, vitamin D, calcium, cortisol, melatonin and whole blood transcriptomics (circadian-associated genes).

Part A, N=24

- A. Subjects with grass pollen allergy and insufficient Vitamin D3
 - a. Subjects taking Vitamin D3 supplementation n = 18
 - b. Subjects on placebo n = 6

Part B: Nasal challenge with allergen involves a total of 46 subjects:

This is divided into 4 groups of subjects given a single dose of Timothy grass pollen (*Phleum P5*) allergen:

The *Phleum P5* is given as 5000 SQ-U = 1µg/100µl/nostril

Subjects with hay fever out of season (n=12)

Subjects with allergic asthma out of season (n=12): half taking no anti-inflammatory drugs, half receiving combined inhaled corticosteroids and long-acting beta-agonists (ICS/LABA)

Non-atopic healthy controls (n=6)

Subjects with hay fever out of season who will trial a novel nasal special sampling probe (SSP) for real time mass spectrometry (n=16)

N= 46

- a. People with hay fever, n = 12
- b. People with allergic asthma, n = 12
- c. Healthy, non-atopic people, n = 6
- d. People with hay fever, n = 16

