APPENDIX 2C

Appendix 2C

Nasal Challenge with Resiquimod (TLR7/8)

Part B. 0.02µg/kg to 0.05µg/kg with Blood Sampling and Nasal Curettage

Single Cohort of up to 46 Volunteers

(12 non-atopic; 12 atopic, 16 allergic asthma, 6 non-allergic asthma)

Each subject given saline control and between resiquimod 0.02 µg/kg to 0.05µg/kg per nostril
4 subjects with asthma initially given half the dose of healthy volunteers

Safety Observations

Nasal mucosal exam, nasal & systemic symptoms and spirometry checked hourly until 10h and at 24h

Screening

- Skin AG pricks
- ECG
- Blood DNA
- Nasal curettage
- Bloods
- Nasal/pharyngeal swab

d-7

Nasal Challenge Saline

d0

Nasal Challenge Resiquimod 0.02 µg/kg to 0.05 µg/kg

d7

Repeat Nasal Challenge (up to 6 from each group) 0.02 µg/kg to 0.05 µg/kg

>6 weeks

Nasal Challenge Procedures

- Initial bilateral lavage at -20m
- PNIF and nasal symptoms: -30m, 15m, 30m, 45m, 1-24h
- Nasal SAM: -30m, -10m, 15m, 30m, 45m, 1-24h
- Nasal curettage: d-7, 8h and 24h (up to 4/timepoint)
- Blood up to 20ml x4: -20m, 4h, 8h & 24h

Nasal SAM, neat:

- Mass Spectrometry
- Lipidomics
- Prostanoids

Nasal SAM, eluate:

- Cytokines & chemokines

Nasal curettage:

- Flow cytometry & transcriptomics

Blood

- Flow cytometry

P
V

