In nasal micro-curettage samples it is possible to measure gene expression, which assesses levels of thousands of mRNA molecules. The [name] group has recently found that there are profound changes in circadian-associated genes in the nasal mucosa after NAC, and that these genes are inhibited by corticosteroids. Circadian genes regulate innate aspects of the immune system by actions involving the BMAL1-CLOCK complex of nuclear transcription factors, receptors and enzymes (70) (71;72). The circadian clock was first identified with regard to lipopolysaccharide(LPS) responses varying with the time of the day, and these circadian responses have been shown to be present in murine macrophage responses to endotoxin (73;74) and more recently in murine inflammatory monocytes (75). In addition, a bronchiolar epithelial clock controls pulmonary inflammation and glucocorticoid action in mice, as shown by genetic ablation of the mouse clock gene *Bmal1* in bronchiolar epithelial cells (76).

Our demonstration in the human nose of allergen-induced changes in circadian-associated genes in the presence of innate inflammatory pathways, suggests that the circadian-associated genes could be controlling gene expression and protein synthesis involved in these innate inflammatory pathways. Furthermore, these allergen-induced circadian changes are reversed by a single preceding oral dose of prednisone, consistent with

known actions of endogenous cortisol (77) (76) implying that the corticosteroid may be acting on circadian-associated genes in order to resolve inflammation.

Since the NAC model with grass pollen is exquisitely sensitive to studying the effects of therapy, we have designed a clinical study to assess whether vitamin D supplementation can alter NAC responses through effects on circadian-associated genes and pathways of inflammation in asthma (78). After a review of the literature we propose a dose of 4000 IU per day for 4 weeks, since this level of dietary supplementation has been safely used in pregnant women and in a large clinical study in asthma (79;80) (65). We shall assess whether there are effects of vitamin D on inflammation produced after NAC: looking at levels of cytokines, chemokines, cells and gene expression, with a focus on circadian-associated genes (78).

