7. STATISTICS AND DATA ANALYSIS

Data and all appropriate documentation will be stored for a minimum of 10 years after the completion of the study, including the follow-up period.

The major data will be levels of cytokines and chemokines in nasal SAM eluates.

We shall perform a test of distribution of data (Shapiro-Wilks test), although nasal levels of chemokines and cytokines are generally non parametric in distribution.

Raw Data:

We shall make plots for individual cytokines with raw data for individuals connected by lines. These “spaghetti plots” generally have different colours for different individuals.

Summary Statistics

Normal data with graphs with means and standard error of means (SEM)

Non-normal data with graphs with medians, quartiles and ranges (box-whisker)

Non-parametric tests are used to compare challenge effects with placebo at different times:
Willcoxon signed-rank test for paired and Mann-Whitney for unpaired data.

The differences from baseline and difference compared with that from placebo (active-placebo) at each time point and the differences from placebo (active-placebo) will be calculated, and the significance determined.

We shall also analyse area under the curve (AUC), by selecting specified times in the early or late phase or for the entire response.

e.g. PGD2 from 10min to 2h

e.g. for IL-4 at 4 to 8h.

A *P* value of <0.05 is considered significant.

Randomization

For the ViDAR study randomization will be supervised by the pharmacy at St Mary’s Hospital. The pharmacy will organise the packaging and have sole access to the randomization codes until the completion of all the clinical aspects of the study.

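### Section 7 has no analysis that measures reproducibility and no error control for transcripts and metabolites, although Section 2.1 leads with validated challenges and biomarker signatures

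*Combined protocol and SAP*

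**What the plan says.** The first objective in Section 2.1 has two parts. One is to develop "robust and reproducible (validated) nasal challenge systems with microbial constituents and allergen". The other reads "To identify biomarker signatures following different challenges". Section 3.1 lists transcriptomics and nasal lining fluid metabolites among the outcomes.

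Repeat challenges appear in Section 3, Group 1 Part B, for the resiquimod arm: "we will invite some of the participants (up to 6 in each group) for a repeat challenge", at least 6 weeks after the prior one. The Appendix 2C diagram agrees: "Repeat Nasal Challenge (up to 6 from each group". Section 8.2 mentions an optional reproducibility element for Part B, but no other agent's design text or schedule contains a repeat.

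Section 7 says that "Non-parametric tests are used to compare challenge effects with placebo at different times", using the "Willcoxon signed-rank test for paired and Mann-Whitney for unpaired data". It adds plots, summary statistics, differences from baseline and placebo, AUCs, and one threshold: a P "value of <0.05 is considered significant". It names cytokines and chemokines as the major data. It contains no agreement measure, no criterion for reproducible or validated, no definition of a signature, no multiplicity rule and no method for transcripts or metabolites. On scale, Section 1.2 describes curettage gene expression as a technique "which assesses levels of thousands of mRNA molecules".

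**The concern.** The analysis plan does not reach the objective that the protocol puts first. Reproducibility is a question of agreement: does a subject who responds strongly once respond strongly again, and how large is the within-subject variation? Tests of challenge against placebo do not address it.

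Signatures are a selection problem across many features. A per-test threshold with no control of the error rate lets a roughly fixed fraction of null features through.

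Sections 1.2 and 2.1 intend these models for biomarker discovery, drug targets and proof-of-pharmacology studies. Within-subject repeatability is what sizes such studies, and a signature with an unknown share of chance findings could misdirect them. Section 2.1 also words the validation aim across all microbial constituents and allergen, whereas the planned data could support it for one agent.

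**Working it through.** The plan gives no sample-size, precision or error-rate figure, so there is nothing to reproduce.

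**1. Where same-subject repeats exist (Section 3)**

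| Agent | Same-subject repeat of the active challenge |
|---|---|
| Resiquimod, Part B | up to 6 in each of 4 groups: 4 × 6 = 24 at most |
| MPLA, poly-ICLC | none designated; Part A gives ascending doses, not repeats |
| Poly-IC | none designated |
| Tuberculin | none; Part A is one dose per subject, and Part B schedules one challenge |
| Allergen, Part B | none designated |
| Allergen, ViDAR | two challenges; 18 subjects take vitamin D in between, 6 take placebo |

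**2. What a difference test says about agreement**

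Take the exact two-sided signed-rank test on first-minus-repeat differences.
- At n=6 the smallest P is 2/2^6 = 0.03125 and the next is 0.0625. P<0.05 therefore needs all six differences to have the same sign.
- If the two challenges have equal means, the chance of non-significance is 1 minus the attainable size: 1 − 0.031 = 0.969 at n=6, and 1 − 0.049 = 0.951 at n=24.

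For differences symmetric about zero, these values do not depend on the within-subject correlation. They are the same at correlation 0 and at a correlation near 1, so the test carries no information on agreement. More subjects do not change that.

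**3. What an agreement measure would give**

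One-way ICC, 2 measurements per subject, observed ICC 0.8 (illustrative): F = (1 + 0.8)/(1 − 0.8) = 9. The limits are (F_L − 1)/(F_L + 1) and (F_U − 1)/(F_U + 1).
- n=6 (5 and 6 df): F_L = 9/5.99 = 1.50 and F_U = 9 × 6.98 = 62.8, giving a 95% CI of 0.20-0.97.
- n=24 (23 and 24 df): F_L = 9/2.28 = 3.94 and F_U = 9 × 2.30 = 20.7, giving 0.60-0.91.
- Fitting group as a factor costs 3 df (20 and 24 df): F_L = 9/2.33 = 3.87 and F_U = 9 × 2.41 = 21.7, giving 0.59-0.91.

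The 95% CI for the within-subject SD is the estimate multiplied by √(n/χ²): 0.64 to 2.20 at n=6, and 0.78 to 1.39 at n=24.

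**4. Null features passing P<0.05**

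Expected count per contrast and time point = number of null features × attainable signed-rank size. The documents give no feature count beyond thousands, so 2,000 and 10,000 are assumptions.

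| n | Attainable size | per 2,000 | per 10,000 |
|---|---|---|---|
| 8 | 0.0391 | 78 | 391 |
| 12 | 0.0425 | 85 | 425 |
| 16 | 0.0443 | 89 | 443 |

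Correlation between features leaves the expected count unchanged but makes it more variable.

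**5. Why adding FDR control to the rank test is not enough at small n**

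At n=8 the smallest signed-rank P is 2/2^8 = 0.0078. Benjamini-Hochberg at 5% needs 0.0078 ≤ 0.05 × k/m, so k/m ≥ 0.156. With m = 10,000, at least 1,563 features would have to tie at the minimum before any passed. At n=16 the smallest P is 0.000031 and k/m ≥ 0.0006, about 7 features in 10,000. The constraint therefore bites in the smaller cohorts.

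**The case against.** The strongest reply is that this is an omission rather than a wrong analysis. That is fair. A reader might infer that the trial would run a Wilcoxon test of first against repeat challenge and call a non-significant result reproducible. Section 7 proposes no such test and says nothing of the kind. The 97% and 95% show why the listed tools cannot fill the gap, not what the investigators will do. Nor is n=6 the whole of the data: with 24 pooled repeats, a mean shift of 0.8 SD of the differences would be missed only 4.5% of the time. That detects drift, but it still does not measure agreement.

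Other stronger readings also fail:
- That repeaters are picked once their first response is known. Section 3 says only that some are invited; Section 8.2 makes the repeat a consent option; and in the non-allergic asthma group all 6 could return.
- That the repeat dose differs from the first. Appendix 2C prints the same range for both.
- That thousands of metabolites are documented for this trial. That remark in Section 1.1 describes earlier mass spectrometry experience.
- That signatures would be mostly chance. This needs the share of true signals, which is unknown, and Section 1.2 reports profound circadian gene changes after allergen challenge.

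Section 7 is written mainly for cytokines and chemokines, so applying P<0.05 to omics data is an inference from its being the only rule given. Chance hits cannot arise in the smallest comparisons: paired n=4 has a minimum P of 0.125, and 6 against 2 has a minimum of 0.071.

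What stands is that neither part of the lead objective has an analysis able to answer it.

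**Conclusion.** The point holds as a gap between Section 2.1 and Section 7. It concerns reproducibility and signatures only; tolerability and time course can be described with the planned summaries.

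The listed tests do not measure agreement, whether 6 or 24 repeats are available. A validated claim could be supported for resiquimod, with useful precision only if the groups are pooled. It has no basis for MPLA, poly-IC, poly-ICLC or tuberculin, and rests on at most 6 pairs for allergen.

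For omics data, the only stated threshold would pass about 4-4.5% of null features per contrast at n=8-16. The resulting counts depend on the assumed number of features, two-sided testing and the signed-rank test. The ICC intervals assume an observed value of 0.8 and full uptake of the repeats; fewer repeats widen them.

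**What to change.** Amend Section 7 in three places.

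1. **Reproducibility.** Report resiquimod log AUC reproducibility as ICC and within-subject CV with 95% CIs. Use pairs in which both challenges were given at the same dose, pooled over groups, with group as a factor, and dose level too where it differs between subjects. This is an analysis restriction and implies nothing about which dose to give.
2. **Scope of the claim.** Limit the reproducible (validated) wording to agents with repeat data. Report the 6 ViDAR placebo pairs as a descriptive allergen estimate with its wide interval.
3. **Transcripts and metabolites.** Replace unadjusted P<0.05 with Benjamini-Hochberg control at 5% FDR per contrast, using a paired moderated linear model on the log scale or an equivalent that is not bound by the minimum rank-test P.

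The cost is protocol wording and analysis time, with no added visits or samples. The downside is fewer named features and a narrower validation claim.

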3.1 STUDY OUTCOME MEASURES

- Clinical symptoms and tolerability
- Inspection of nasal mucosa by a clinician: erythema, discharge, ulceration
- Mucosal lining fluid cytokines and chemokines
- Blood and nasal flow cytometry and transcriptomics
- Nasal lining fluid metabolites

4. PARTICIPANT ENTRY

4.1 PRE-REGISTRATION EVALUATIONS: SCREENING HISTORY AND TESTS

Before patients are considered for inclusion in the study we shall consider whether they have asthma or hay fever, or a history of latent tuberculosis (TB), or whether they are healthy volunteers (HVs) with none of these conditions.

Screening tests may include intra-epidermal skin allergen prick tests and an intradermal tuberculin skin test.

4.2 MIXED INCLUSION & EXCLUSION CRITERIA (FOR ALLERGEN CHALLENGE ARMS ONLY)

General: for all subjects

- Males and females aged 18 to 60 years
- Current non-smokers for last year, maximum of 10 cigs per month, with a smoking history of <5 pack years

- Body mass index in the range 18-39
- No systemic illnesses that might affect nasal immune responses
- No recent viral infections in past month: including colds and flu.
- No nasal anatomical abnormalities, sinus infections, polyps, nasal mucosal abnormalities
- No prescribed anti-inflammatory drug therapy

A. Healthy non-atopic volunteers

- No clinical history of allergic rhinitis, allergic asthma or eczema.
- Negative skin prick tests to a range of 6 common aeroallergens: cat, dog, grass pollen, tree pollen, house dust mite, fungal spores
- Normal blood eosinophil count

B. Atopic subjects with Timothy Grass Pollen sensitivity & Vitamin D Insufficiency

- A clinical history of seasonal grass pollen allergic rhinitis: sneezing, running and itching nose, nasal drip in the UK grass pollen summer season (May-July).
- Specific allergy confirmed by positive intra-epidermal skin prick test to Timothy grass pollen extract (Soluprick, *Phleum pratense*; ALK, Horsholm, Denmark), a positive reaction being a raised wheal of diameter ≥ 3 mm larger than a negative saline control.
- Vitamin D insufficiency: serum levels of 25-hydroxy vitamin D₃ (25-OHD₃) <30ng/ml or <30 μ g/L or <75nmol/L
 - No use of sun lamps, vitamin D supplements (including fish oils), no holidays abroad in sunny locations (including beach holidays and skiing) for the duration of participation
 - No clinical history of tree pollen allergy from February to April

C. Asthmatic subjects with Timothy Grass Pollen sensitivity

- Seasonal grass pollen allergic rhinitis: sneezing, running and itching nose, nasal drip in the UK grass pollen summer season (May-July).
- Specific allergy confirmed by positive intra-epidermal skin prick test to Timothy grass pollen extract (Soluprick, *Phleum pratense*; ALK, Horsholm, Denmark), a positive reaction being a raised wheal of diameter ≥ 3 mm larger than a negative saline control.
- Half the asthmatics have clinical history and diagnosis of asthma, requiring therapy with occasional inhaled beta-agonists, but no inhaled corticosteroids for the past 28 days. Half the asthmatics receive regular combined inhaled corticosteroids and long-acting beta-agonists (ICS/LABA)

4.3 MIXED INCLUSION & EXCLUSION CRITERIA (FOR TLR AGONIST ARM ONLY)

General: for all subjects

- Males and females aged 18 to 60 years
- Current non-smokers for last year, maximum of 10 cigs per month, with a smoking history of <5 pack years
- Body mass index in the range 18-39
- No systemic illnesses that might affect nasal immune responses
- No recent viral infections in past month: including colds and flu.

- No nasal anatomical abnormalities, sinus infections, polyps, nasal mucosal abnormalities
- No prescribed anti-inflammatory drug therapy

A. Healthy non-atopic volunteers

- No clinical history of allergic rhinitis, allergic asthma or eczema.
- Negative skin prick tests to a range of 6 common aeroallergens: cat, dog, grass pollen, tree pollen, house dust mite, fungal spores
- Normal blood eosinophil count
- Normal baseline forced expiratory volume (FEV1) i.e. $\geq 80\%$
- Negative methacholine challenge ($PC_{20} > 8\text{mg/ml}$)

B. Atopic subjects with Timothy Grass Pollen sensitivity

- A clinical history of seasonal grass pollen allergic rhinitis: sneezing, running and itching nose, nasal drip in the UK grass pollen summer season (May-July).
- Specific allergy confirmed by positive intra-epidermal skin prick test to Timothy grass pollen extract (Soluprick, *Phleum pratense*; ALK, Horsholm, Denmark), a positive reaction being a raised wheal of diameter $\geq 3\text{mm}$ larger than a negative saline control.
- Normal baseline forced expiratory volume (FEV1) i.e. $\geq 80\%$

C. Asthmatic subjects with Timothy Grass Pollen sensitivity

- Physician diagnosed asthma up to stage 2 BTS/GINA guidelines
- Seasonal grass pollen allergic rhinitis: sneezing, running and itching nose, nasal drip in the UK grass pollen summer season (May-July).
- Specific allergy confirmed by positive intra-epidermal skin prick test to Timothy grass pollen extract (Soluprick, *Phleum pratense*; ALK, Horsholm, Denmark), a positive reaction being a raised wheal of diameter $\geq 3\text{mm}$ larger than a negative saline control.
- Baseline forced expiratory volume (FEV1) $\geq 75\%$
- Positive methacholine challenge ($PC_{20} < 8\text{mg/ml}$)

D. Asthmatic subjects with no allergies

- Physician diagnosed asthma up to stage 2 BTS/GINA guidelines
- No clinical history of allergic rhinitis or eczema
- Negative skin prick tests to a range of 6 common aeroallergens: cat, dog, grass pollen, tree pollen, house dust mite, fungal spores
- Normal blood eosinophil count
- Baseline forced expiratory volume (FEV1) $\geq 75\%$
- Positive methacholine challenge ($PC_{20} < 8\text{mg/ml}$)

EXCLUSION CRITERIA

Nasal and Respiratory

- Recent infections in past 14 days before screening: especially upper respiratory tract illnesses (including colds and influenza), sore throats, sinusitis, infective conjunctivitis.
- Lower respiratory tract infection in past 28 days
- Signs or symptoms of significant nasal anatomical defects, hypertrophy of turbinates, major septum deviation, nasal polyposis or recurrent sinusitis
- Nasal mucosal defects, injury, ulceration
- Previous nasal or sinus surgery

Therapy

- Medical therapy other than that permitted for contraception.
- Treatment with local or systemic corticosteroids during the previous 2 months (other than low dose inhaled corticosteroids for asthmatic subjects)
- Anti-inflammatory therapy: including non-steroidal anti-inflammatory drugs (NSAIDs)

Concomitant diseases

Clinically significant diseases are not permitted

- tuberculosis at any stage in life
- active infectious disease
- cardiovascular diseases
- respiratory (other than hay fever or asthma where specified)
- hepatic, gastrointestinal, renal, endocrine, infective, haematological, autoimmune, rheumatological, neurological, dermatological,
- neoplastic conditions
- metabolic diseases and extreme obesity
- depression and psychiatric disorders

Miscellaneous

- Non-smokers: up to 10 cigarettes a year is permitted
- Participation in a therapeutic drug trial in the prior 30 days.
- Inability or unwillingness to use contraception if the patient is a female of child-bearing age.
- Pregnant or breast feeding women
- Inability to provide informed consent

